7.1.1 Sub-group analyses

Sub-group analyses will investigate the variation in treatment effects between:

- i. patients with paroxysmal and non-paroxysmal AF,
- ii. individual centres,
- iii. different ablation devices,
- iv. complete and incomplete lesion sets,
- v. different cardiac surgical procedures.

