4. INTERVENTION

4.1 Randomisation

Eligible patients who fulfil the inclusion criteria, have provided full written consent and have had sufficient time for discussion and consideration, will be randomised (in a 1:1 ratio) to one of two groups. They will receive either their routine cardiac surgery with no additional procedure or their routine cardiac surgery with an adjunct maze procedure.

Patient allocations will be computer generated by the trial statistician and will be in random permuted blocks of variable lengths, stratified by surgeon and by planned cardiac procedure (CABG, aortic valve, mitral valve, combined procedure).

On the day of surgery, when the patient is in the anaesthetic room, the local centre will register the participating patient with Papworth Hospital R&D Unit by telephone or fax.

Patient details, surgeon and planned cardiac procedure will be recorded by R&D unit staff not otherwise directly involved with the trial. Once registration is complete the group allocation will be released to the surgical team who will also be responsible for completing the surgical data forms. The group allocation will not be made available to any other staff who are directly involved with the trial.

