4.2 Control intervention

Patients randomised to the control arm will receive their pre-operative management, elective cardiac surgery (without an adjunct maze procedure) and post-operative management according to standardised hospital protocols. All subsequent management, follow up and data collection will be identical to the experimental intervention group.

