4.4.1 Management of patients before, during and after surgery

This will be undertaken according to the local site's normal practice irrespective of randomisation. The only exceptions will be processes required to maintain blinding of the patient, cardiologist and quality of life interviewer, which will be described in the Trial Management Protocol.

4.4.2 Conducting and reporting on the adjunct maze procedure $^{(14)}$ and defining the prescribed lesion set $^{(6)}$

Clinicians are free to carry out the lesions that they would perform in normal practice. Details of the ablation procedure and all lesions will be documented. The full lesion set is illustrated in Figure 1.

Recently published guidelines for reporting data and outcomes for surgical treatment of atrial fibrillation ⁽¹⁴⁾ will be followed.

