Appendix 4: Data to be collected

Stage of trial	Data to be collected				
i. Baseline screening prior	Confirmation of eligibility and adherence to				
to consent	inclusion/exclusion criteria				
ii. Baseline post consent	 Basic demographics Symptoms & severity, including angina class, NYHA class and palpitations Type and duration of AF Current medication Details of previous attempts at cardioversion (consistent) 				
	 with ACC/AHA/ECS 2006 Guidelines) EuroSCORE Underlying cardiac disease including coronary lesions, valve lesions and ventricular function Details of planned operation Baseline HRQoL (EuroQoL, SF-36 & NYHA) 4 day ECC 				
iii. Peri-procedural	 4-day ECG Detailed operative data Ablation device used (in intervention group) Details of lesions used (in intervention group) Immediate post-operative electrocardiogram (ECG) Mortality, morbidity, length of stay Resources (theatre time, device costs, consumables, length of stay in ICU and cardiac ward) 				
iv. At discharge	 ECG Cardiac medication, including anticoagulants and antiarrhythmics Any pacemaker implant EuroQoL Resource use Adverse events 				
v. 6 weeks post-surgery (routine clinic visit)	 Stroke diagnosis and stroke specific/thromboembolic event questionnaire Mortality Details of medication (anticoagulant,antiarrhythmic) Cardioversion plan if appropriate EuroQoL Resource use Adverse events 				
vi. 6 months post-surgery	 Details of medication (anticoagulant, antiarrhythmic) Stroke diagnosis and stroke specific questionnaire/thromboembolic event Mortality HRQoL (EuroQoL, SF-36 & NYHA questionnaires) Details of any cardioversion and outcome Details of any pacemaker insertion Resource use Adverse events 				
vii. 12 & 24 months post- surgery	 Details of medication (anticoagulant, antiarrhythmic) Stroke diagnosis and stroke specific and thromboembolic event questionnaire. Mortality HRQoL (EuroQoL, SF-36 & NYHA questionnaires) Details of any cardioversion and outcome Details of any pacemaker implant 4-day ECG monitoring Resource use 				

Version no: 3.0 date: 9 October 2009

	Adverse events
iix. Annually (by telephone – funding not requested)	 Details of medication (anticoagulant, antiarrhythmic) Stroke diagnosis and stroke specific questionnaire/thromboembolic event
	 Mortality HRQoL (EuroQoL, SF-36 & NYHA questionnaires) Details of any cardioversion and outcome Details of any pacemaker insertion Resource use Adverse events

Version no: 3.0 date: 9 October 2009 Page 25 of 39

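### Lesion-set completeness is known only in the maze arm and only after allocation, so item iv of section 7.1.1 cannot give a randomised treatment-effect subgroup; the device item has a weaker form of the problem

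*Protocol*

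**What the plan says.** Protocol section 7.1.1 opens with "Sub-group analyses will investigate the variation in treatment effects between" and lists five factors. Item iii is "different ablation devices" and item iv is "complete and incomplete lesion sets".

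Other sections determine what is known about these two factors:

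- **Control arm (section 4.2).** Controls have "elective cardiac surgery (without an adjunct maze procedure", so they have no device and no lesions.
- **Data collected (Appendix 4, peri-procedural stage).** The entries are "Ablation device used (in intervention group" and "Details of lesions used (in intervention group", each restricted to the maze arm.
- **Timing (section 4.1).** "Once registration is complete the group allocation will be released to the surgical team". This happens while the patient is in the anaesthetic room. Registration records patient details, surgeon and planned cardiac procedure. Randomisation is stratified by surgeon and planned procedure.
- **Choice of lesions (section 4.4.2).** "Clinicians are free to carry out the lesions that they would perform in normal practice". The text to Figure 1 expects that some patients will not have the full set.
- **Choice of device (sections 3.4 and 4.3).** Investigators use their institution's usual device. The device and energy source are recorded patient by patient, with some subgroup analysis to follow.
- **Caveat (section 1, Introduction).** The trial is said to be neither designed nor powered to tell devices apart. No such caveat is given for lesion sets.

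**The concern.** A treatment effect here is maze against control. To say that it differs between two kinds of patient, one must be able to sort patients in both arms into those kinds, on something allocation cannot have influenced. AF type (item i) meets that test. Lesion-set completeness does not: nobody knows which controls would have received a complete set.

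If completeness depends on the patient, the operation or the surgeon, maze patients with complete and incomplete sets may differ in their chance of sinus rhythm (SR) whatever the lesions did. Reported under a heading about variation in treatment effects, that difference would read as evidence on technique. A larger sample would estimate the wrong quantity more precisely; it would not remove the bias.

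**Working it through.** **1. The plan's own figure.** Section 3.5.1 gives 176 per group for 45% against 30% SR at 12 months (80% power, two-sided 5%). The usual two-proportion formula is

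n = [1.96·√(2·0.375·0.625) + 0.842·√(0.45·0.55 + 0.30·0.70)]² / 0.15²,

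which gives 163 per group, or 176 with the continuity correction. The stated figure reproduces. Its only use here is to supply the 30% control rate and the 15-point effect as yardsticks.

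**2. Which contrasts exist for item iv.**

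- Maze against control among patients with a complete set: not available, because no control can be put in this class.
- Maze against control among patients with an incomplete set: not available, for the same reason.
- Maze-complete against maze-incomplete: available, not randomised.
- Each maze subset against all controls: available, not randomised, since a selected subset is set against an unselected arm.

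**3. How large a false difference could be.** The protocol gives no data on selection, so the following values are assumed:

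- Half the patients have a good and half a poor prognosis.
- Control SR is 40% and 20%, mean 30%.
- Maze adds 15 points in everyone, giving 55% and 35%. Completeness therefore has no true influence.
- A complete set is made in a share q of good-prognosis and 1 − q of poor-prognosis patients, so half of all sets are complete.

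Then SR with a complete set = 55q + 35(1 − q), SR with an incomplete set = 55(1 − q) + 35q, and the false difference is 20(2q − 1) points.

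| Complete set in good / poor prognosis | SR complete / incomplete | Apparent effect against all controls (30%) | False difference |
|---|---|---|---|
| 50% / 50% | 45% / 45% | 15 / 15 points | 0 |
| 60% / 40% | 47% / 43% | 17 / 13 points | 4 |
| 70% / 30% | 49% / 41% | 19 / 11 points | 8 |
| 80% / 20% | 51% / 39% | 21 / 9 points | 12 |
| 100% / 0% | 55% / 35% | 25 / 5 points | 20 |

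**4. What classified controls would do.** Take the 70/30 row. Controls who would have had a complete set have SR 0.7·40 + 0.3·20 = 34%; the others have 0.3·40 + 0.7·20 = 26%. The effects are 49 − 34 = 15 and 41 − 26 = 15 points, and the false difference disappears.

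**5. Item iii.** If a surgeon or centre has one routine device, its controls can be given that label through the surgeon or centre, and the effect within that device is a randomised comparison. Two gaps remain. The protocol does not guarantee one device per surgeon, and section 3.4 ties the analysis to the device used in each patient. Even with the label, one device's effect comes from different surgeons and centres than another's.

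**The case against.** The strongest reply is that section 7.1.1 is only a short list. It names no model and no comparator, and a statistical analysis plan, not shown here, could label items iii and iv descriptive or confine them to the maze arm. That stands for the labelling. It does not answer the data problem: such a plan cannot recover an intended lesion set that was never recorded. Appendix 4 does list details of the planned operation at baseline, but nothing says that these include intended lesions or device.

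A second reply is that lesion choice follows normal practice and may be settled before surgery, so a reader should not infer that every choice is made during the operation. This is fair; the protocol does not say when the choice is made. But what Appendix 4 captures is the lesions made, which follow allocation, and only in one arm.

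A third reply concerns devices. A reader might infer that no treatment effect by device can be estimated at all. The documents do not support that: sections 4.3 and 4.1 (usual institutional device, stratification by surgeon) leave a route to randomised within-device effects, and the Introduction already disclaims comparison of devices.

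**Conclusion.** The point holds for lesion sets and, in weaker form, for devices. As written, item iv promises variation in treatment effect on a factor that controls do not have and that arises after allocation; what can be computed is an observational contrast.

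The size is unknown. Under the assumed prognoses, moderate to strong selection gives false differences of 4 to 12 points, and none if completeness is unrelated to prognosis. A reader might take 20 points, more than the 15-point design effect, as the likely error. That figure requires every good-prognosis patient and no poor-prognosis patient to receive a complete set, and nothing in the protocol suggests selection of that strength.

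The primary comparison and the sample size are untouched. This is a correction to secondary subgroup analyses, worth making because the information needed must be captured before allocation.

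**What to change.** 1. In section 4.1 and Appendix 4, add two fields to registration, completed for every patient in both arms before allocation is released: intended lesion set (complete or incomplete) and intended device. This records intention only and changes no clinical management.
2. In section 7.1.1, define items iii and iv on these intended values.
3. Label any analysis by actual lesion set or actual device as descriptive, non-randomised and maze-arm only. If the fields cannot be added, make at least this change. It is also all that can be done on lesion sets for patients randomised before the fields exist.

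The cost is two form fields and revised wording. There are three limits. Where intended and actual lesions or device differ, the contrast is diluted. Effects within each intended subgroup are randomised, but differences between subgroups remain observational, since surgeons and patients differ. Precision will be low: with 176 per arm split evenly (88 per cell) and SR of 45% and 30% in both subgroups, the standard error of the difference in effects is √[2(0.45·0.55 + 0.30·0.70)/88] = 0.102, so 80% power needs a difference of about 2.80·0.102 = 0.286, or 29 points. The change makes the subgroup analysis valid; it does not make it powerful.

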7.2 Economic analysis

An NHS perspective will be adopted for the economic analysis. For both groups patientspecific resource use data will be collected until all patients have completed at least 12months post-randomisation (mean 2 years, maximum 3 years). According to current Department of Health guidelines ⁽¹⁹⁾ an annual discount rate of 3.5% will be applied to all costs incurred between 12 and 24 months post-randomisation. The following resource areas will be measured and valued.

i. Costs of Surgery

The average cost of the initial cardiac surgery will be based on the capital cost of the equipment, variable costs, staff and overhead costs involved. The extra capital cost of the RF ablation device will be annualised and apportioned, where relevant, on a per patient basis. Staff and overhead costs will be allocated according to theatre time and annual patient throughput. The use of variable consumable costs (e.g. blood products, IV heparin) will also be recorded prospectively on a per patient basis.

ii. Costs after surgery

Resource use will be monitored from surgery through to at least 12 months postrandomisation. Information will be collected on hospital admissions due to adverse events including readmissions to hospital, any further cardiac procedures and pacing, GP and outpatient visits and cardiac-related medication. Patients will be asked to record medications taken, inpatient and outpatient visits and any procedures in a purposedesigned questionnaire to be administered alongside the quality of life measures. Patient responses will be validated against hospital and primary care records. Unit costs will be taken from the hospital accounting system for each participating centre and nationally published estimates. ^(20, 21)

iii. Economic outcome measurement

At baseline, on discharge and at 6 weeks, 6 months, 12 months and 24 months post surgery all patients will be asked to complete the EuroQoL questionnaire, including the EQ-5D. The social tariff for the EQ-5D, as estimated by Dolan *et al* will be applied to each patient's self-reported classification in order to calculate utility values.⁽²²⁾ Using actual rather than nominal times of assessment, and assuming a linear change in values between time points, patient-specific utility curves up to 24-months post randomisation will be calculated. A value of zero will be applied at the date of death for those patients who died.

iv. Economic Analysis

The QALYs experienced by each patient to 24-months post randomisation will be calculated as the area under their utility curve to 24-months or time of death, whichever occurs first. In order to adjust for differences in baseline utilities a linear regression will be fitted to the utilities post treatment, with baseline utility and treatment group as explanatory variables. Treatment effects will be taken from the treatment group coefficient of this regression. For patients who do not complete all EuroQoL/resource use measurements and are censored the methods of Willan and Lin ⁽²³⁾ will be used to estimate mean QALYs and costs.

The incremental cost-effectiveness ratio (ICER), calculated as the ratio of the difference in costs and QALYs, will be estimated using the sample means. In order to generate confidence intervals without assuming any parametric form for the distribution of the costs, bootstrapping will be used to resample patients and repeat the calculations described above 1000 times. ⁽²⁴⁾ Measurements will be summarised as the mean and 95% confidence interval, estimated using bootstrapping. The bootstrap samples for the treatment comparison will also be plotted on the cost-effectiveness plane. In addition, cost-effectiveness acceptability curves (CEAC) for these comparisons will be plotted. The CEAC plots the probability that a functional test is cost-effective if we are willing to pay at most $\pounds X$ per QALY on the vertical axis, against X on the horizontal axis. Sensitivity analysis will be used to explore the impact of the deterministic variables within the economic analysis (e.g. unit cost estimates discount rate).

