6.3 Data collection during and after surgery

(See Appendix 3 for the Schedule of Events and Appendix 4 for the full list of data to be collected.)

Data collection will be based on the recommendations of Shemin et al ⁽¹⁴⁾ and include procedural details – including the lesion set in the experimental group.

Version no: 3.0 date: 9 October 2009

Data to be collected after surgery will include: mortality, stroke/thromboembolic events, medications, EuroQoL, health-related quality of life, cardioversion plan if appropriate, 4-day ECG recordings, resource use, adverse events.

Data will be collected during surgery, at discharge, 6 weeks after surgery (at a routine service visit), at 6, 12 and 24 months after surgery during out-patient research visits and annually thereafter by telephone follow-up.

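### Section 7.2's resource-use collection rule conflicts with the 24-month QALY horizon, the visit schedule and the 18-month accrual, and no cost horizon is fixed for the ICER

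*Protocol*

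**What the plan says.** Protocol section 7.2 opens with a collection rule: resource-use data are gathered "until all patients have completed at least 12months post-randomisation (mean 2 years, maximum 3 years"). Its subsection on costs after surgery repeats the minimum: "Resource use will be monitored from surgery through to at least 12 months postrandomisation".

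On discounting, the same section says "an annual discount rate of 3.5% will be applied to all costs incurred between 12 and 24 months post-randomisation". It gives no rule for costs after 24 months and does not mention discounting of QALYs.

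The QALY horizon is fixed: "The QALYs experienced by each patient to 24-months post randomisation will be calculated as the area under their utility curve to 24-months", or to death if earlier. The ratio is then defined: "The incremental cost-effectiveness ratio (ICER), calculated as the ratio of the difference in costs and QALYs, will be estimated using the sample means". For censored patients with incomplete EuroQoL or resource-use measurements, a cited inverse-weighting method "will be used to estimate mean QALYs and costs".

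Section 6.3 schedules data collection "at 6, 12 and 24 months after surgery during out-patient research visits", with annual telephone contact afterwards. Appendices 3 and 4 list resource use at the 24-month visit, and Appendix 2 runs 24-month visits to month 46. Section 3.5.2 gives 18 months of recruitment.

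**The concern.** The rule in section 7.2 is a calendar cut-off: collection ends when the last patient reaches 12 months, so each patient's cost window depends on when he or she was recruited. The QALY window is the same 24 months for all. A team following section 7.2 literally would stop collecting costs a year before the last 24-month visit. Most patients' second-year costs would then have to be estimated.

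The rule also allows collection beyond 24 months. Costs from that period would have no matching QALYs and no discount rule. Because the protocol never states the period over which costs enter the ratio, two analysts could compute different ICERs from the same data and both claim to follow the plan. Cost per QALY is the lead secondary objective, and section 3.5.1 judges it against £20,000 to £30,000 per QALY.

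**Working it through.** **Inputs.** Surgery counts by month come from Appendix 2, months 5 to 22: 15, 16, 16, 20, 25, 25, 25, 25, 18, 20, 24, 24, 25, 24, 25, 24, 24, 25, total 400. Patients are randomised on the day of surgery (section 4.1), so time from surgery and time from randomisation coincide. The last 12-month visit is in month 34 and the last 24-month visit in month 46.

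**1. The plan's own mean and maximum.** With uniform accrual over R months and a cut-off when the last patient reaches 12 months, mean follow-up is 12 + R/2 and the maximum is 12 + R.
- R = 24: mean 24, maximum 36. This reproduces the stated figures.
- R = 18 (section 3.5.2): mean 12 + 9 = 21, maximum 30. It does not.
- Appendix 2 counts, cut-off month 34: minimum 34 − 22 = 12, maximum 34 − 5 = 29, mean 7,983 patient-months / 400 = 19.96.
- Appendix 2 counts, cut-off month 46: minimum 24, mean 31.96, maximum 41. This does not fit either.

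**2. Completeness of 24-month costs at month 34.**
- Only patients operated on by month 10 have reached 24 months: 15 + 16 + 16 + 20 + 25 + 25 = 117.
- Short of 24 months: 400 − 117 = 283, or 70.75%, before deaths and losses.
- Cross-check on planned 24-month visits by month 34: 12 + 14 + 14 + 18 + 22 + 23 = 103 of 360 (29%).
- The mean of 19.96 includes windows longer than 24 months. The excess is 5×15 + 4×16 + 3×16 + 2×20 + 1×25 = 252 patient-months. Capped at 24, the mean is (7,983 − 252) / 400 = 19.3 months.

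**3. Discounting.** Section 3.5.1's cost limit reproduces at the upper threshold: 0.0833 × £30,000 = £2,499, against the stated £2,500. The year-2 factor is 1/1.035 = 0.966. If a share f of the QALY gain falls in year 2 (an assumption, ranged 0 to 1), the discounted gain is 0.0833 × (1 − 0.0338f).
- f = 0: 0.0833, and £2,500 gives about £30,010 per QALY.
- f = 0.5: 0.0819 (1.7% smaller), about £30,530.
- f = 1: 0.0805 (3.4% smaller), about £31,060.

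**4. Horizon, illustration only.** The protocol gives no annual cost difference. Assume a constant c of £250 to £1,000 per year, higher in the maze arm, and a QALY gain of 0.0833.
- Raw costs to month 34 instead of 24 months for all: c × (19.96/12 − 2) / 0.0833 = about −£1,000 to −£4,000 per QALY.
- Three years of costs for every patient: c / 0.0833 = about +£3,000 to +£12,000 per QALY.
- If the maze arm saved money each year, both signs would reverse.

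These are unweighted sums. They show how far the choice of horizon could matter and do not predict the trial's result.

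**The case against.** A reader might infer that the ICER will divide costs and QALYs measured over different periods. The documents do not support that. Section 7.2 sets a window for collecting data; it does not say costs are summed over that window. Several features point to an intended 24-month estimate: the discount rule ends at 24 months, the resource-use questionnaire accompanies the quality-of-life measures, and the inverse-weighting method covers both costs and QALYs. Annual collection after 24 months is marked in Appendix 4 as unfunded, and section 2 foresees separate longer-term modelling that could use it.

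Nor do the documents say that QALYs will go undiscounted. That is inferred from silence, the detail may sit in an analysis plan not shown, and section 7.2 already varies the discount rate in sensitivity analysis. Unequal windows also do not imply imbalance between arms: allocation is 1:1 in permuted blocks, so window lengths should be similar in both.

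All of this stands. It can also be said that 12 months is only a minimum, so that the rule permits 24 months for everyone. That does not rescue the sentence. If every patient had at least 24 months, the mean could equal 24 only if nobody had more, which contradicts a three-year maximum. The rule as written therefore implies that some patients have less than 24 months of cost data. Inverse weighting can handle censoring, but it needs a stated horizon and is a poor substitute for data already scheduled.

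**Conclusion.** The point holds as an internal contradiction and an unstated cost horizon. The collection rule conflicts with the 24-month QALY horizon, with the scheduled 24-month resource-use visits and with 18-month accrual. Its mean and maximum cannot be obtained from the protocol's own schedule.

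The 71% without complete 24-month costs is conditional: it assumes collection really stops at month 34 and recruitment follows Appendix 2. If the visit schedule is followed to month 46, every surviving patient still in follow-up has 24 months of costs and this loss disappears. The effect on the ICER cannot be sized from the documents. The discounting question is minor, at most 3.4% of the QALY gain.

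This is a should-fix. It concerns a secondary objective, and neither primary outcome (sinus rhythm at 12 months, quality-adjusted survival over 2 years) depends on the cost window.

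**What to change.** In section 7.2:
- Replace both statements of a 12-month minimum, and the stated mean and maximum, with collection of resource use to 24 months post-randomisation for every patient.
- State that costs and QALYs in the ICER both run to 24 months or death, with inverse weighting for patients censored before then.
- Apply the 3.5% rate to both costs and QALYs in year 2.
- Reserve any costs after 24 months for the longer-term modelling.
- Run the ICER analysis after the last 24-month visit (month 46 in Appendix 2).

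The cost is protocol wording only. The 24-month resource-use data are already scheduled, and the two-year QALY outcome has to wait for month 46 in any case.
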